9.2. Sample Size Considerations

9.2.1. Sample Size Assumptions

[figure not shown]
The study is not powered to detect pre-defined differences. In Cohort 1, approximately 30 subjects and up to a maximum of 36, will be randomised into the study to either GSK2982772 or placebo in a 2:1 ratio to ensure that approximately 24 evaluable subjects complete the study.

In Cohort 2, approximately 24 subjects and up to a maximum of 32, will be randomised into the study to either GSK2982772 or placebo in a 3:1 ratio to ensure that approximately 20 evaluable subjects complete the study.

A subject is considered evaluable if they have completed at least one post-treatment biopsy.

The primary objective of the study is safety and tolerability, where there will be 20 subjects randomised to GSK2982772 60 mg BID and 18 subjects randomised to GSK2982772 60 mg TID. Using a Bayesian approach to determine the confidence interval around an observed safety event, we would assume a flat Beta (1, 1) prior, and if we were to observe one safety event in 20 then the posterior distribution would be Beta (2, 20), as outlined below in [Figure 4](#).

Figure 4 One Event in 20 Subjects: Beta (2,20) Distribution

Thus, we can be 95% certain that the true probability of the safety event lies between 0.01 and 0.24. Similarly, if we were to observe one safety event in 18 then the posterior

distribution would be Beta (2, 18), thus we can be 95% certain that the true probability of the safety event lies between 0.01 and 0.26.

For supportive information the properties of the secondary endpoint PLSS have also been considered. Assuming a standard deviation of 25%, it is estimated that the lower and upper bounds of the 95% confidence interval for the difference between GSK2982772 60 mg BID (n=20) and placebo (n=10) in percentage change in index lesion PLSS will be within approximately 17.1% of the point estimate, and that the lower and upper bounds of the 95% confidence interval for the difference between GSK2982772 60 mg TID (n=18) and placebo (n=6) in percentage change in index lesion PLSS will be within approximately 17.5% of the point estimate.

[figure not shown]

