9. STATISTICAL CONSIDERATIONS AND DATA ANALYSES

9.1. Hypotheses

The primary objective of the study is to investigate the safety and tolerability of GSK2982772 60 mg BID and 60 mg TID following 12 weeks of treatment. No formal statistical hypotheses will be conducted to assess this objective.

If appropriate, comparisons between the GSK2982772 arms and the placebo arm will be made to investigate the secondary inflammatory, mechanistic and efficacy objectives. Trends over time will be investigated for both treatment arms along with associations between each of the parameters.

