9.2.2. Sample Size Sensitivity

A sample size sensitivity analysis has been conducted on the primary endpoint to investigate the different safety event rates. If the number of subjects who complete the 12 weeks is lower than anticipated, then the true incidence rates of safety events that could not be ruled out (as outlined in Section 9.2.1) would change. These changes are outlined in [Table 4](#).

Table 4 Sample Size Sensitivity

GSK2982772 subjects completing the study	Number of a particular safety event observed with GSK2982772	Upper limit of exact 95% CI indicating that a true incidence rate of x% could not be ruled out
20	0	16.1%
20	1	23.8%
20	2	30.4%
18	0	17.6%
18	1	26.0%
18	2	33.1%
16	0	19.5%
16	1	28.7%
16	2	36.4%

Similarly, for supportive information a sensitivity analysis of the precision of the secondary endpoint percentage change in PLSS has been performed to assess the impact of varying variability and numbers of GSK2982772 and placebo subjects [Figure 5](#).

Figure 5 Sample Size Sensitivity for Percentage Change in PLSS

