9.3.2. Interim Analysis

In line with routine pharmacovigilance, an internal GSK Safety Review Team (SRT) which will include members of the GSK2982772 project team, will review blinded safety data, including clinical laboratory parameters and adverse events, at appropriate intervals during the period of study conduct.

In both cohorts, once an appropriate number of subjects randomised to GSK2982772 have completed Day 43 (Week 6), the PLSS data will be reviewed in an unblinded manner by a Data Review Committee (DRC) consisting of the GSK Project Physician Lead (PPL), the study statistician, the study pharmacokineticist, the PRR DPU Head, the Early Development Lead (EDL), the Safety Review Team (SRT) leader, or their designees on an ongoing basis. A physician external to the GSK2982772 project team may also be involved in the data review. Additional inflammatory biomarkers, clinical and mechanistic endpoints (e.g., target engagement) may be reviewed if available. No other member of the GSK core study team will be unblinded to this data. The primary purpose of these reviews will be to monitor PLSS changes for internal decision making purposes. A data review charter will identify the specific GSK individuals involved, outline in detail the activities of this review and how the integrity of the study will be maintained.

A formal interim analysis will be conducted after the completion of Cohort 1 and will only include those subjects randomised to a BID dosing regimen. The purpose of the interim analysis is primarily to provide the project team and key GSK stakeholders with an early indication of the safety and efficacy from the trial, and to facilitate decision making regarding the subsequent clinical development of GSK2982772.

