9.3.4. Secondary Analyses

Comparisons between treatment groups on any changes observed will be conducted for the secondary endpoints if deemed appropriate, e.g. changes in the mean target engagement, changes in inflammatory markers and percentage change in index lesion PLSS be statistically analyzed using a MMRM (repeated measures mixed effects model) comparing each GSK2982772 arm with placebo at each time point. If sufficient numbers of subjects are enrolled with a BSA >5% then the proportion of subjects achieving PASI 50/75/90 at Day 85 (12 Weeks), will be statistically analysed using a Generalised Estimating Equations (GEE) model comparing each GSK2982772 arm with placebo at

each time point if appropriate. Similar analyses will be conducted for other secondary endpoints if deemed appropriate.

The relationship between each of the mechanistic endpoints and also with the clinical endpoints may also be graphically presented and analysed using an appropriate statistical model identifying any trends. The model will determine whether the mechanistic effect significantly explains or predicts the effect on the other mechanistic or clinical endpoints (e.g., index lesion PLSS score). This may be conducted through comparing statistical models incorporating different explanatory terms (i.e. mechanistic endpoints) with the 'null' model (no mechanistic endpoints); or if deemed appropriate, multivariate statistical methods may also be applied to determine the relationship between the key endpoints. The consistency in the changes over time between the endpoints will also be assessed.

In addition, based on the data that we observe in the study, probabilities of success will be determined, where the definition of success will be dependent on the endpoint. For example, what is the probability that we would observe a certain percentage change in PLSS (i.e., comparatory rate), based on the data that we have observed in the study.

GSK2982772 plasma concentrations will be summarised descriptively by Day and nominal time point by dosing regimen.

Further details regarding the statistical analysis will be outlined in the Reporting and Analysis Plan (RAP).

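### Section 9.2.1: the PLSS confidence-interval half-widths (17.1% BID, 17.5% TID) do not follow from the printed placebo numbers (10 and 6); they fit an unstated pooled placebo group of 16

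*Protocol*

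**What the plan says.** Section 9.2.1 describes the precision of a secondary endpoint, percentage change in index lesion PLSS, as supportive information in a study without formal power. The inputs are an SD ("Assuming a standard deviation of 25", in percent) and a 95% interval ("lower and upper bounds of the 95% confidence interval for the difference"). Two comparisons follow:

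- BID: "60 mg BID (n=20) and placebo (n=10) in percentage change in index lesion PLSS will be within approximately 17.1% of the point estimate"
- TID: "60 mg TID (n=18) and placebo (n=6) in percentage change in index lesion PLSS will be within approximately 17.5% of the point estimate"

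The group sizes are the planned within-cohort allocations: about 30 subjects at 2:1 give 20 and 10, and about 24 at 3:1 give 18 and 6.

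On the comparator, section 9.1 says that, if appropriate, "comparisons between the GSK2982772 arms and the placebo arm will be made to investigate the secondary inflammatory, mechanistic and efficacy objectives". Section 9.3.4 describes a repeated-measures model "comparing each GSK2982772 arm with placebo at each time point". Neither says whether the placebo subjects of the two cohorts are combined. Section 9.3.2 plans an interim analysis after Cohort 1 that "will only include those subjects randomised to a BID dosing regimen". Section 9.2.2 adds that "a sensitivity analysis of the precision of the secondary endpoint percentage change in PLSS has been performed" and refers to Figure 5, which is not reproduced in the text available for this review.

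**The concern.** The two printed half-widths are almost equal, although one comparison has 10 placebo subjects and the other 6. With so small a placebo group, the TID interval should be clearly wider than the BID interval.

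What is at stake is what the stated precision describes. If the comparison is within cohort, readers are promised tighter intervals than the data can give, most of all for TID. If placebo is pooled, the precision depends on combining subjects from two separately randomised cohorts with different allocation ratios (2:1 and 3:1) and dosing frequencies, and the sentence does not say so. The Cohort 1 interim has no Cohort 2 placebo subjects, so 17.1% cannot apply there under either reading.

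**Working it through.** **Inputs** (all from section 9.2.1): common SD 25 percentage points; two-sided 95% interval; BID 20 vs 10; TID 18 vs 6.

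**Formula.** Half-width = c × SE, with SE = 25 × √(1/n₁ + 1/n₂). The protocol does not name the method, so three choices of c were tried: normal (1.960), pooled-variance t on n₁ + n₂ − 2 df, and Welch t with Satterthwaite df.

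**Step 1: the printed numbers**

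| Comparison | SE | Normal | Pooled-variance t | Welch t | Printed |
|---|---|---|---|---|---|
| 20 vs 10 | 9.682 | 18.98 | 2.048 (28 df) → 19.83 | 2.100 (18.11 df) → 20.33 | 17.1 |
| 18 vs 6 | 11.785 | 23.10 | 2.074 (22 df) → 24.44 | 2.278 (8.61 df) → 26.85 | 17.5 |

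No entry reaches the printed value. Even the narrowest choice, the normal interval, exceeds it by 18.98 − 17.1 = 1.9 points for BID and 23.10 − 17.5 = 5.6 points for TID.

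**Step 2: could another SD explain it?** With a common SD, the ratio of the two half-widths does not depend on its value. At the printed numbers the TID/BID ratio is 23.10/18.98 = 1.22 (normal), 24.44/19.83 = 1.23 (pooled-variance t) or 26.85/20.33 = 1.32 (Welch). The printed ratio is 17.5/17.1 = 1.02. Put another way, with pooled-variance t the BID figure would need an SD of 21.6 and the TID figure an SD of 17.9.

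**Step 3: other settings at within-cohort numbers (BID, TID)**

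- Error df of 50 or 51 from one model over all arms: about 19.4 and 23.7.
- A 90% interval: 15.9 and 19.4 (normal) or 16.5 and 20.2 (t).
- Maximum enrolment (24 vs 12, 24 vs 8): 17.3 and 20.0 (normal) or 18.0 and 20.8 (t).

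None gives the pair 17.1 and 17.5.

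**Step 4: 16 placebo subjects (10 + 6) in both comparisons**

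| Comparison | SE | Normal | Pooled-variance t | Welch t | Printed |
|---|---|---|---|---|---|
| 20 vs 16 | 8.385 | 16.43 | 17.04 (34 df) | 2.036 (32.29 df) → 17.07 | 17.1 |
| 18 vs 16 | 8.590 | 16.84 | 17.50 (32 df) | 2.038 (31.53 df) → 17.51 | 17.5 |

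Welch t rounds to both printed values. Pooled-variance t matches TID and gives 17.0 for BID. The SE ratio is 8.590/8.385 = 1.024, in line with the printed ratio.

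**The case against.** The arithmetic at the printed numbers is not in dispute. The best case on the other side is that pooling was plainly intended and only the placebo n in brackets is mislabelled. Section 9.1 speaks of a single placebo arm, section 9.3.4 compares each active arm with placebo, and 16 is exactly 10 + 6. As context only, the amendment log shows a superseded BID figure of 20.3, which is the Welch value for 20 vs 10, changing to 17.1 when the TID cohort was added. On this reading the half-widths are right, and the large TID discrepancy describes a comparison nobody meant to make. This makes pooling the likelier explanation, but it remains an inference.

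Sixteen with Welch t is also not the only numerical match. A normal interval with 14 placebo subjects gives 17.07 and 17.46, and t on 51 df with 15 gives 17.14 and 17.55. Neither 14 nor 15 is a planned group, so 16 remains the best explanation. Every match still needs a common placebo group well above the printed 10 and 6.

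Two limits stand. Figure 5 and the study schematics could not be seen, so the remark that pooling is unstated covers the readable text only. Leaving the comparator's definition to the analysis plan would not be a fault in itself; the fault is that one sentence prints n, SD and half-widths that disagree. The consequence is also modest, since the figures are supportive.

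**Conclusion.** The concern holds. Taken with SD 25% and the printed group sizes, both half-widths in section 9.2.1 are wrong, and "approximately" cannot cover the TID gap.

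- **If placebo is pooled:** the half-widths stand (17.07 and 17.51 by Welch t), and the placebo n should be 16 in both comparisons.
- **If the comparison is within cohort:** BID should be 19.8 (pooled-variance t) or 20.3 (Welch), which is 2.7 or 3.2 points above the printed value. TID should be 24.4 or 26.8, which is 6.9 or 9.3 points above.

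Pooling is the more probable reading, but the readable text does not state it. The mismatch does not depend on which reading is right. The calculation assumes a common SD, a simple two-group comparison of means and the planned allocation; the protocol does not name the interval method. Enrolment, randomisation and decision rules are unaffected, so this should be fixed but does not threaten the design.

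**What to change.** In section 9.2.1, state which comparison the precision describes, name the interval method, and make the numbers agree:

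1. **Pooled placebo:** print placebo n=16 for both comparisons, keep 17.1% and 17.5%, name Welch t, and say that placebo is combined over two separately randomised cohorts. Give the within-cohort figures alongside.
2. **Within cohort:** keep n=10 and n=6, and replace 17.1% and 17.5% with 20.3% and 26.8% (Welch t) or 19.8% and 24.4% (pooled-variance t).

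Under either option it would help to add that a half-width of about 20% (19.8% or 20.3%) applies to the BID-only Cohort 1 interim. Section 9.3.2 promises no precision there, so this is a clarification and not a correction. Confirm that Figure 5 in section 9.2.2 uses the same group sizes and method.

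The cost is wording only, with no change to enrolment, randomisation or analysis. Under option 2 the stated precision becomes less favourable.

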9.2.2. Sample Size Sensitivity

A sample size sensitivity analysis has been conducted on the primary endpoint to investigate the different safety event rates. If the number of subjects who complete the 12 weeks is lower than anticipated, then the true incidence rates of safety events that could not be ruled out (as outlined in Section 9.2.1) would change. These changes are outlined in [Table 4](#).

Table 4 Sample Size Sensitivity

GSK2982772 subjects completing the study	Number of a particular safety event observed with GSK2982772	Upper limit of exact 95% CI indicating that a true incidence rate of x% could not be ruled out
20	0	16.1%
20	1	23.8%
20	2	30.4%
18	0	17.6%
18	1	26.0%
18	2	33.1%
16	0	19.5%
16	1	28.7%
16	2	36.4%

Similarly, for supportive information a sensitivity analysis of the precision of the secondary endpoint percentage change in PLSS has been performed to assess the impact of varying variability and numbers of GSK2982772 and placebo subjects [Figure 5](#).

Figure 5 Sample Size Sensitivity for Percentage Change in PLSS

9.2.3. Sample Size Re-estimation or Adjustment

No sample size re-estimation or adjustment will be conducted.

9.3. Data Analysis Considerations

9.3.1. Analysis Populations

All Subjects Population: The ‘All Subjects Population’ is defined as subjects who were screened for the study. This population is used for the summary of selected accountability data.

Safety Population: The ‘Safety Population’ is defined as subjects who receive at least one dose of study medication. This population is used for the summary of all data including demography, safety, efficacy and exploratory data but excluding PK data.

Pharmacokinetic Population: The 'PK Population' is defined as subjects in the 'Safety' population who received an active dose and for whom a pharmacokinetic sample was obtained and analysed. This population is used for the summary of PK data only. Any PKPD analyses will be conducted on the Safety population such that subjects receiving placebo can be included.

9.3.2. Interim Analysis

In line with routine pharmacovigilance, an internal GSK Safety Review Team (SRT) which will include members of the GSK2982772 project team, will review blinded safety data, including clinical laboratory parameters and adverse events, at appropriate intervals during the period of study conduct.

In both cohorts, once an appropriate number of subjects randomised to GSK2982772 have completed Day 43 (Week 6), the PLSS data will be reviewed in an unblinded manner by a Data Review Committee (DRC) consisting of the GSK Project Physician Lead (PPL), the study statistician, the study pharmacokineticist, the PRR DPU Head, the Early Development Lead (EDL), the Safety Review Team (SRT) leader, or their designees on an ongoing basis. A physician external to the GSK2982772 project team may also be involved in the data review. Additional inflammatory biomarkers, clinical and mechanistic endpoints (e.g., target engagement) may be reviewed if available. No other member of the GSK core study team will be unblinded to this data. The primary purpose of these reviews will be to monitor PLSS changes for internal decision making purposes. A data review charter will identify the specific GSK individuals involved, outline in detail the activities of this review and how the integrity of the study will be maintained.

A formal interim analysis will be conducted after the completion of Cohort 1 and will only include those subjects randomised to a BID dosing regimen. The purpose of the interim analysis is primarily to provide the project team and key GSK stakeholders with an early indication of the safety and efficacy from the trial, and to facilitate decision making regarding the subsequent clinical development of GSK2982772.

9.3.3. Primary Analyses

All safety evaluations will be based on the Safety population. Clinical interpretation will be based on the review and displays of adverse events, clinical laboratory values, vital sign measurements and 12-lead ECG monitoring.

9.3.4. Secondary Analyses

Comparisons between treatment groups on any changes observed will be conducted for the secondary endpoints if deemed appropriate, e.g. changes in the mean target engagement, changes in inflammatory markers and percentage change in index lesion PLSS be statistically analyzed using a MMRM (repeated measures mixed effects model) comparing each GSK2982772 arm with placebo at each time point. If sufficient numbers of subjects are enrolled with a BSA >5% then the proportion of subjects achieving PASI 50/75/90 at Day 85 (12 Weeks), will be statistically analysed using a Generalised Estimating Equations (GEE) model comparing each GSK2982772 arm with placebo at

each time point if appropriate. Similar analyses will be conducted for other secondary endpoints if deemed appropriate.

The relationship between each of the mechanistic endpoints and also with the clinical endpoints may also be graphically presented and analysed using an appropriate statistical model identifying any trends. The model will determine whether the mechanistic effect significantly explains or predicts the effect on the other mechanistic or clinical endpoints (e.g., index lesion PLSS score). This may be conducted through comparing statistical models incorporating different explanatory terms (i.e. mechanistic endpoints) with the 'null' model (no mechanistic endpoints); or if deemed appropriate, multivariate statistical methods may also be applied to determine the relationship between the key endpoints. The consistency in the changes over time between the endpoints will also be assessed.

In addition, based on the data that we observe in the study, probabilities of success will be determined, where the definition of success will be dependent on the endpoint. For example, what is the probability that we would observe a certain percentage change in PLSS (i.e., comparatory rate), based on the data that we have observed in the study.

GSK2982772 plasma concentrations will be summarised descriptively by Day and nominal time point by dosing regimen.

Further details regarding the statistical analysis will be outlined in the Reporting and Analysis Plan (RAP).

9.3.5. Other Analyses

9.3.5.1. Exploratory Analyses

All exploratory endpoints will be descriptively summarized, graphically presented and listed appropriately. Further details can be found in the RAP.

10. STUDY GOVERNANCE CONSIDERATIONS

10.1. Posting of Information on Publicly Available Clinical Trial Registers

Study information from this protocol will be posted on publicly available clinical trial registers before enrollment of subjects begins.

10.2. Regulatory and Ethical Considerations, Including the Informed Consent Process

The study will be conducted in accordance with all applicable regulatory requirements, and with GSK policy.

The study will also be conducted in accordance with ICH Good Clinical Practice (GCP), all applicable subject privacy requirements, and the guiding principles of the current version of the Declaration of Helsinki. This includes, but is not limited to, the following:

- IRB/IEC review and favorable opinion/approval of the study protocol and amendments as applicable
- Obtaining signed informed consent
- Investigator reporting requirements (e.g. reporting of AEs/SAEs/protocol deviations to IRB/IEC)
- GSK will provide full details of the above procedures, either verbally, in writing, or both.
- Signed informed consent must be obtained for each subject prior to participation in the study
- The IEC/IRB, and where applicable the regulatory authority, approve the clinical protocol and all optional assessments, including genetic research.
- Optional assessments (including those in a separate protocol and/or under separate informed consent) and the clinical protocol should be concurrently submitted for approval unless regulation requires separate submission.
- Approval of the optional assessments may occur after approval is granted for the clinical protocol where required by regulatory authorities. In this situation, written approval of the clinical protocol should state that approval of optional assessments is being deferred and the study, with the exception of the optional assessments, can be initiated.

